7.1.5.1. Statistical Methodology Specification

Endpoint / Variables

 See above
Model Specification

 See above
Model Checking & Diagnostics

 “Bayesian Statistics Best Practice at GSK – Clinical Trials using Bayesian Inference” (effective 20-Apr-2017) gives guidance on model checking and diagnostics that would be applicable to the MCMC modelling in this study.
Model Results Presentation

 See above
Subgroup Analyses

 Not planned.
Sensitivity and Supportive Analyses

 See above. Only the final (chosen) model form would be used to produce the Tables/Listings/Figure outputs supporting the CPSR. If the joint modelling strategy fails then an alternative strategy would be to derive the RV

dysfunction status for each participant (using the same criteria) and analyse the collection of derived binary outcomes, accounting for the repeated measures made on each participant (e.g. logistic regression modelling techniques). The final logit model (including any covariates) would be used to determine the probabilities (and differences) for the sets of “pre and post” dose Ang II reference values to be fed into the decision-making criteria. Any such approach would be documented in the CSR.

7.2. Secondary Efficacy Analyses

7.2.1. Endpoint / Variables

The variables to be included in the secondary pharmacodynamic analysis are the same as for the primary pharmacodynamic analysis, with the addition of the following independent variables:

- Ang(1-7) on Study Days 1, 2 and 3
- (Optionally) Ang(1-5) on Study Days 1, 2 and 3 (if the correlation between Ang(1-7) and Ang(1-5) values is not too high – otherwise the analysis would not be expected to add additional insights/value)
- Note: The planned modelling using similar techniques to the primary analysis for the Ang II/Ang(1-7) response on Study Days 1, 2 and 3 will not be attempted.

Incidence rates would be assessed across

- i) the entire study (the outcome taking the value of the worst case observed) and
- ii) on an individual visit basis (Note: Screening and Day 1 data would be combined and labelled as Day 1; the worst case outcome used in any combination)

The following rates would be assessed

- Incidence rates of ARDS diagnosis
- Incidence rates of PCD or ACP (any right ventricular dysfunction; regardless of PCD or ACP severity level)
- Incidence rates of PCD (Moderate PCD (not severe enough to qualify as ACP))
- Incidence rates of Non-severe ACP
- Incidence rates Severe ACP

Additionally, the worst case PCD/ACP diagnosis across the study would be combined with the ARDS diagnosis to form the following categories

- ARDS and No PCD or ACP
- ARDS and PCD
- ARDS and Non-Severe ACP
- ARDS and Severe ACP

7.2.2. Summary Measure

For the Ang(1-7) and Ang(1-5) endpoints described above:

- The posterior predictive probability of RV dysfunction for pre-determined “pre-dose” Ang II and Ang(1-7) values (or Ang(1-5)),

- The posterior predictive probability of RV dysfunction for pre-determined “post-dose” Ang II and Ang(1-7) values (or Ang(1-5)), and
- The difference between the two (Note: Although the difference will still be computed as Pre-Post for Ang(1-7) and Ang(1-5) negative values would be a favourable outcome).

For the incidence rate variables

- The At Risk population would be used to filter the individuals going into the subsequent analysis dataset
- For rates relating to an individual visit
 - The big N value would not represent distinct participants but instead represents the maximum number of visits in the analysis dataset (derived by counting the number of subject visits where any ARDS or PCD/ACP assessment was made (expecting three visits per subject – but may reduce if subjects withdraw/die before day 3))
 - the little n value would represent the number of completed visits for that item
 - Freq. represents the number of positive occurrences (Subjects with a Yes response)
 - Rate (%) = $100 * \text{Freq.} / \text{n}$ [little n]
 - The 95% CI for the rate (%) should be derived using Wilson Score interval with continuity correction methodology
- For rates relating to the entire study
 - The big N value represents the number of participants for whom an ARDS or PCD/ACP assessment was made at any time in the study
 - Freq. represents the number of positive occurrences (Subjects with a Yes response)
 - Rate (%) = $100 * \text{Freq.} / \text{N}$ [big N]
 - The 95% CI for the rate (%) should be derived using Wilson Score interval with continuity correction methodology

Any modifications to the above would be described in the CSR.

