Exploratory	Will be described in the reporting and analysis plan

Given that the hypothesis to this study is that RAS-mediated pulmonary vasoconstriction may be reduced through the dual action of ACE2 by simultaneously reducing Ang II and forming Ang(1-7) (see Section 3.2), an important secondary analysis will be to explore the joint effect of both Ang II and Ang(1-7) as related to RV dysfunction. That is to say, in addition to exploring the individual hypotheses that Ang II is deleterious to RV function and that Ang(1-7) is beneficial, a model will be developed that integrates the combined effects of these two mediators, since the expected effect of treatment with ACE2 is that both will change. Several models may be analysed in order to explore the exact nature of the relationship between the dual action of changes in Ang II and Ang(1-7) and the probability of RV dysfunction as measured by PASP and RV size ratio.

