In order to evaluate the estimated effect of administering rhACE2 on RV outcomes (via its effect on the RAS peptides), predictions for the probability of RV dysfunction will be calculated for specific, pre-determined values of RAS peptide measurements that represent reasonable estimates for each RAS peptide both before and after dosing with rhACE2 in this patient population. These values will be hereafter referred to as *reference values* (the first reference value, hereafter referred to as the *pre-dose reference* and the second reference value, hereafter referred to as the *post-dose reference* reflect). Note: the terminology "pre-dose" and "post-dose" should not be taken to imply that investigational product is used in this study; these values should be taken as being borrowed from that interventional study. Furthermore, the term "reference values" in this context should not be interpreted as upper or lower limits to the normal range. They represent the best guess available for a patient's typical experience before and after rhACE2 administration.

Initially, the basic model described below would be attempted. If model convergence issues are encountered with that model it is unlikely that more complicated models involving covariates would fit, and covariate exploration may not be attempted. However, if covariate exploration is attempted the addition of covariates would be dependent on a combination of changes in DIC and expert judgement (including the biological rationale for the covariate and/or global structures of other statistical models fitted to comparable data types). To simplify reporting only model outputs from the final selected model would be formally reported (included in the CPSR), but a description / short justification for the selected model would be included in the CPSR.

At the time of writing, the reference values for Ang II (and for completeness Ang(1-7) and Ang(1-5)) were as follows:

	ANG II (pg/mL)	ANG 1-7 (pg/mL)	ANG 1-5 (pg/mL)
	Optional endpoint		
"Pre-dose" reference value	30.0	2.0	n/a
"Post-dose" reference value	8.0	30.0	n/a

An additional sensitivity analysis (to be computed alongside the above) in case the reference study values are discordant with the observed values will use the observed data to determine the references as follows

Sensitivity	ANG II (pg/mL)	ANG 1-7 (pg/mL)	ANG 1-5 (pg/mL) Optional endpoint

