Sensitivity “Pre-dose” reference value	Upper Quartile of Observed ANG II	Lower Quartile of Observed ANG 1-7	Lower Quartile of Observed ANG 1-5
Sensitivity “Post-dose” reference value	Lower Limit of Quantification	Upper Quartile of Observed ANG 1-7	Upper Quartile of Observed ANG 1-5

The relationship between Ang II (as the explanatory variable) and the joint bivariate distribution of PASP and RV size ratio (the outcome variables) will be analysed using a Bayesian multivariate linear regression model.

The multivariate normal model is specified as follows:

$$\begin{pmatrix} y_{it1} \\ y_{it2} \end{pmatrix} \sim MVNormal \left(\begin{pmatrix} \mu_{it1} \\ \mu_{it2} \end{pmatrix}, \Sigma \right)$$

where y_{itj} represents the observed value for the i th participant, the t th time-point and the j th outcome (i.e. $j = 1$ representing PASP and $j = 2$ representing RV size ratio), μ_{itj} represents the expected value for the i th participant, t th time-point ($t = 1, 2, 3$) and the j th outcome ($j=1$ and $j=2$ as above), and Σ represents a variance-covariance (vcov) matrix for the two outcome variables.

The expected values, μ_{itj} , are modelled as follows:

$$\mu_{itj} = \alpha_j + \beta_j x_i + \gamma_{tj} z_{it}$$

where:

- α_j is the intercept term for the j th outcome (i.e. PASP or RV size),
- β_j represents the vector of slope coefficients for all participant-level variables in the model for the j th outcome,
- x_i represents the vector of observed participant-level variables values for the i th participant (if applicable – initial model structures would not involve such covariates but Age at Screening and Sex would be added first to be consistent with the study protocol),
- γ_{tj} represents the matrix of slope coefficients for all timepoint-level variables in the model for the j th outcome at time-point t ,
- z_{it} represents the matrix of observed time-point-level variables for the i th participant at time-point t (e.g. log10- transformed RAS).

The vcov matrix Σ is specified within each study participant, as a Kronecker product of the inter- and intra-marker vcov matrices Sigma and Tigma , respectively:

$$\Sigma = \text{Sigma} \otimes \text{Tigma}$$

(the notation \otimes represent the Kronecker product)

The $\mathbf{y}_{i=1,2}$ inter-marker vcov matrix

$$\text{Sigma} = \begin{pmatrix} \sigma_{y_1}^2 & \sigma_{y_1 y_2} \\ \sigma_{y_1 y_2} & \sigma_{y_2}^2 \end{pmatrix}$$

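### SAP 7.2.2 labels a negative Pre-Post difference favourable for Ang(1-7) and Ang(1-5), but with the SAP's own reference values the favourable sign is positive

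*SAP*

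**What the plan says.** SAP 7.2.2 defines the secondary peptide summary as three quantities: a predicted probability of RV dysfunction at the pre-dose reference, the same at the post-dose reference ("The posterior predictive probability of RV dysfunction for pre-determined “post-dose” Ang II and Ang(1-7) values (or Ang(1-5)), and"), and the difference between them. It then fixes both the order of subtraction and its reading: "Although the difference will still be computed as Pre-Post for Ang(1-7) and Ang(1-5) negative values would be a favourable outcome".

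The reference values are in SAP 7.1.5, where they are meant to "represent reasonable estimates for each RAS peptide both before and after dosing with rhACE2 in this patient population". In the order Ang II, Ang(1-7), Ang(1-5), in pg/mL, the pre-dose row reads "reference value 30.0 2.0 n/a" and the post-dose row "reference value 8.0 30.0 n/a". In the sensitivity set the pre-dose reference is "Lower Quartile of Observed ANG 1-7" for Ang(1-7) and "Lower Quartile of Observed ANG 1-5" for Ang(1-5); the post-dose reference is the upper quartile for each.

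Protocol 10.3.1 gives the expected directions, the "individual hypotheses that Ang II is deleterious to RV function and that Ang(1-7) is beneficial".

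**The concern.** RV dysfunction is the bad outcome. If rhACE2 raises Ang(1-7) and Ang(1-7) protects the right ventricle, predicted risk should be lower at the post-dose reference, and subtracting post from pre then gives a positive number. The note says the opposite.

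It appears to allow for Ang(1-7) moving in the opposite direction to Ang II. That allowance is already made in the reference values, where Ang II falls from 30.0 to 8.0 and Ang(1-7) rises from 2.0 to 30.0. The note turns the sign a second time.

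The Ang(1-7) association is a secondary objective (SAP 2.2). Modelling of the ratio has been dropped (SAP 2.1), and the Ang(1-5) and joint-model tables are conditional outputs (SAP 10.10.8). The single-peptide Ang(1-7) model in Table 5.5 is therefore the one secondary peptide model that is not conditional, and SAP 7.1.5 says it may be used to support the primary analysis. Under the note, a protective association could be described as unfavourable and a harmful one as favourable.

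**Working it through.** **1. The sign by definition.** Let D = P(dysfunction | pre-dose reference) − P(dysfunction | post-dose reference). Then D > 0 if and only if predicted risk is lower at the post-dose reference. This holds for any peptide and any model.

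**2. The sign by the order of the references.** For Ang(1-7) the pre-dose value is the lower one (2.0 < 30.0; lower quartile < upper quartile). If more Ang(1-7) means less dysfunction, P at the low value exceeds P at the high value, so D > 0. For Ang II the pre-dose value is the higher one (30.0 > 8.0). If more Ang II means more dysfunction, again D > 0. The note would suit a high-minus-low contrast (here Post-Pre) or the peptide's slope, but SAP 7.2.2 specifies Pre-Post on probabilities.

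**3. Reproducing the plan's own figures.** Inputs from Protocol 12.5.4: PASP mean 38, SD 8; RV size ratio mean 0.61, SD 0.15; correlation between them 0.5; log(Ang II) mean 2.78, SD 1.74. References 55.4 and 7.1 pg/ml (Protocol 12.5.3). At concentration c:

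- z = (ln c − mean log) / SD log
- conditional mean of outcome j: m_j + r_j·s_j·z
- conditional variance of outcome j: s_j²(1 − r_j²); covariance: s₁s₂(0.5 − r₁r₂)
- P(c) = 1 − Pr(PASP ≤ 40 and ratio ≤ 0.6), bivariate normal

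With r = 0.6 for both outcomes, z(55.4) = (4.015 − 2.78)/1.74 = 0.710 and z(7.1) = (1.960 − 2.78)/1.74 = −0.471. Then P = 86.0% and 51.9%, a difference of 34.1 points against 33.9 in Protocol Table 1b. With r = 0.3 for both, 73.1 − 58.2 = 14.9 against 14.9. All nine Table 1b scenarios agree within 0.3 points.

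**4. The same formula for Ang(1-7).** The documents give no Ang(1-7) distribution. Assumed: log-normal, geometric mean √(2.0 × 30.0) = 7.7 pg/mL, log-SD 1.74, r = −0.3 with both outcomes (protective). Then z(2.0) = −0.778 and z(30.0) = +0.778. Mean PASP is 39.9 and 36.1 mmHg; mean ratio is 0.645 and 0.575. P = 73.9% and 54.0%, so D = +19.9 points.

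Varying the geometric mean over 2, 7.7 and 30 pg/mL and the log-SD over 1.0, 1.74 and 2.5:

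| Assumed correlation with both outcomes | D, Ang(1-7) 2.0 to 30.0 | D, quartile references |
|---|---|---|
| −0.6 (protective) | +24.5 to +71.0 | +40.3 |
| −0.3 (protective) | +12.8 to +35.7 | +17.3 |
| +0.3 (harmful) | −12.8 to −35.7 | −17.3 |
| +0.6 (harmful) | −24.5 to −71.0 | −40.3 |

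Every protective case is positive and every harmful case negative. The exact ±19.9 mirror at the central assumption arises because 7.7 is the geometric midpoint of the two references; at a geometric mean of 2 and the same log-SD the pair is +21.1 and −17.5.

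**5. Sign conventions elsewhere.** Protocol 12.5.3 subtracts P at 7.1 from P at 55.4 and counts a large positive value as success, which is Pre-Post with positive favourable. Protocol 10.3.3, for the first interim analysis, calls the difference positive when risk at the pre-dose value is the lower of the two, which is Post-Pre. SAP 7.1.2 gives no order.

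**The case against.** The strongest reply concerns consequence. The error is in one interpretive note. The model, the reference values, both predicted probabilities and the computed difference are unaffected. The interim analyses are cancelled (SAP 3.1), no formal hypotheses are tested (SAP 2.4), and the 15% and 30% criteria are written for Ang II. The Ang(1-7) model is supportive (SAP 7.2.5.1) and the Ang(1-5) model optional. Table 5.5 shows the reference concentrations in its subtitles and is to report the probability of RV dysfunction at each (SAP 7.2.2, 10.10.8), so a careful reader can see which concentration carries the higher risk. All of this stands.

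A reader might infer that the secondary results would inevitably be reported backwards, or that Tables 5.4 and 5.5 would contradict each other. The documents do not support that. The programming notes for these tables call for no favourable or unfavourable label, and the table shells are not included. If both hypotheses hold, both tables show a positive difference. A conflict would appear only in text that applies the note.

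The opposite sign in Protocol 10.3.3 does not rescue the note, because SAP 7.2.2 states Pre-Post explicitly. It does show that the convention needs to be settled across the documents.

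For Ang(1-5) the objection has some force. There is no fixed reference pair, and no passage says the peptide is beneficial; SAP 7.2.5.1 only expects it to correlate highly with Ang(1-7). The sign logic still follows from the quartile order if Ang(1-5) is taken to act in the same direction.

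**Conclusion.** The note in SAP 7.2.2 is wrong as written. For Ang(1-7), and for Ang(1-5) if it is modelled and assumed beneficial, a favourable result under Pre-Post is positive. Anyone who applies the note would reverse the interpretation of a secondary objective.

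This conclusion rests only on RV dysfunction being adverse, on the stated order of subtraction and on the order of the reference values. It does not depend on the illustrative sizes, which describe a hypothetical association and not the damage done by the note.

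It is a moderate correction to make before reporting. It does not invalidate any estimate, and no formal decision rule turns on it.

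**What to change.** Replace the note in SAP 7.2.2 with wording such as: *The difference is computed as Pre-Post for all peptides. Because the pre-dose reference is the lower concentration for Ang(1-7) and Ang(1-5), a positive difference (lower predicted probability of RV dysfunction at the post-dose reference) is favourable, as for Ang II.*

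- Add this as a footnote to Tables 5.5 and 5.6 only.
- Table 5.7 needs its own statement. Under SAP 7.2.5.2 the joint-model contrast is pre-dose against post-dose Ang II at each Ang(1-7) value, so the explanation about the lower concentration would misdescribe it.
- State the same order and reading (Pre-Post, positive favourable) in SAP 7.1.2, in line with Protocol 12.5.3, and record that the first-interim text in Protocol 10.3.3 uses the opposite sign.

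The cost is a few sentences in the SAP and some table footnotes. No new data, modelling or recalculation is needed.

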7.2.5.3. Analysis of disease incidence within the mechanically ventilated population

The incidence of ACP and PCD in the population will be presented as summary tables, by study day, and overall (i.e. diagnosis at any time during the three-day study period).

Descriptive statistics (N (population), #Occurrences (Freq.), number at risk (n), Incidence Rate and 95% CI for Rate (methodology for 95% CI: Wilson Score interval with continuity correction))

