10.10.6. Pharmacodynamic and Biomarker Tables

Pharmacodynamic and Biomarker: Tables					
No.	Population	IDSL / Example Shell	Title	Programming Notes	Deliverable [Priority]
Echocardiography					
3.1.	Evaluable	PD_T1 (ECHO)	Summary of Echocardiogram Measurements by Timepoint	Two separate statistics tables: 1) for continuous, 2) for qualitative echo measurements.	SAC 1
3.2.	Evaluable	SM_T1 (ECHO)	Within- and Between-Subject Variability of Continuous Echocardiogram Measurements		SAC 1
RAS Biomarkers					
3.3.	Evaluable	PD_T2 (RAS)	Summary of RAS Biomarker Measurements by Timepoint	Present results for levels and log transformed in two separate tables.	SAC 1
3.4.	Evaluable	SM_T1 (RAS)	Within- and Between-Subject Variability of RAS Biomarker Measurements		SAC 1

Participant Status and Other Clinical Assessments: Tables					
No.	Population	IDSL / Example Shell	Title	Programming Notes	Deliverable [Priority]
Disease Diagnosis Status					
4.1.	At risk	OCA_T1 (DISEASE_INCIDENCE)	Summary of ARDS, PCD and ACP Incidence Rates by Timepoint and Study	Create two tables: 1) summarizing of number of the cases, where patient may contribute multiple times and 2) with overall incidence rates including the joint categories. Note: Shell does not contain all items to be displayed	SAC 1

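### SAP 7.2.2 counts N and n for individual-visit ARDS, PCD and ACP rates in visits, although other sections point to one row per study day; define the row and its 95% CI

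*SAP*

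**What the plan says.** SAP 7.2.2 gives separate rules for rates relating to an individual visit and rates relating to the entire study. For the individual-visit rates:

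- Big N is a count of visits, with three expected per subject: "The big N value would not represent distinct participants but instead represents the maximum number of visits in the analysis dataset".
- The denominator of the rate is also in visits: "the little n value would represent the number of completed visits for that item".
- Freq. is described as positive occurrences, but the bracket that follows explains it in terms of subjects answering Yes.
- The rate is 100 × Freq. / n, and "The 95% CI for the rate (%) should be derived using Wilson Score interval with continuity correction methodology". Nothing is said about one participant supplying several visits.

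The programming note for Table 4.1 (SAP 10.10.6) asks for two tables, the first "summarizing of number of the cases, where patient may contribute multiple times".

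Other places describe rows by day. SAP 7.2.1 leaves at most one record per participant per day: "Screening and Day 1 data would be combined and labelled as Day 1". SAP 7.2.5.3 says: "The incidence of ACP and PCD in the population will be presented as summary tables, by study day, and overall". It explains overall as a diagnosis at any time in the three days, and labels N as the population and n as the number at risk. The title of Table 4.1 is "Summary of ARDS, PCD and ACP Incidence Rates by Timepoint and Study".

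For whole-study rates, SAP 7.2.2 counts N in participants.

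**The concern.** On a row for a single study day, visits and participants are the same thing. A statement that the count is not of distinct participants therefore has content only across days. A programmer who applies SAP 7.2.2 literally could build one row from all visits and put a binomial interval on it. Up to three days of the same participant would then count as independent observations. The SAP does not treat the underlying measurements that way: its primary model (7.1.5) gives PASP and RV size ratio an AR(1) correlation over the three days.

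The incidence of ACP and PCD is a secondary objective, and Table 4.1 is the summary table listed for it. At stake is whether the visit-level rows of that table show more precision than the participants can support, or carry an N that does not belong to the row.

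**Working it through.** **The plan's own precision figure.** Protocol 10.1 gives ±5 percentage points for ACP incidence, as a 95% Wald half-width at 10% in 150 participants: 1.96 × √(0.10 × 0.90 / 150) = 0.048, or 4.8 points. This reproduces the stated 5. Its unit is participants.

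**Inputs.** The 10% rate is the protocol's planning value, and three visits per participant is the SAP's expectation. The documents give no within-participant correlation (ICC), no final number enrolled after early termination, and no 30% rate. Those are assumed, with ICC from 0 to 0.9 and 25 or 50 participants.

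**Wilson interval with continuity correction** (p = x/n, q = 1 − p, z = 1.96):

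- lower = [2np + z² − 1 − z√(z² − 2 − 1/n + 4p(nq + 1))] / [2(n + z²)]
- upper = [2np + z² + 1 + z√(z² + 2 − 1/n + 4p(nq − 1))] / [2(n + z²)]

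With 10% positive in 50 participants:

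- One day, 5/50: lower = (12.84 − 8.81) / 107.68 = 3.7%; upper = (14.84 + 9.49) / 107.68 = 22.6%; width 18.9 points.
- Three days pooled, 15/150: lower = (32.84 − 14.70) / 307.68 = 5.9%; upper = (34.84 + 15.11) / 307.68 = 16.2%; width 10.3 points.

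**Effect of repeated visits if pooled.** The design effect is 1 + (3 − 1) × ICC. At ICC 0.3, 0.5 and 0.7 it is 1.6, 2.0 and 2.4, so 150 visits carry the information of about 94, 75 and 63 independent ones.

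Simulated coverage of the nominal 95% interval (beta-binomial data; at least 100,000 replicates per pooled cell):

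| Participants, rate | ICC 0 | 0.1 | 0.3 | 0.5 | 0.7 | 0.9 | Single-day row |
|---|---|---|---|---|---|---|---|
| 50, 10% | 96% | 94% | 90% | 86% | 82% | 78% | 97% |
| 25, 30% | 96% | 94% | 89% | 85% | 81% | 77% | 97% |
| 25, 10% | 98% | 97% | 94% | 91% | 87% | 84% | 97% |

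**Effect on N if read by day.** With 50 participants and all visits done, big N is 3 × 50 = 150, while n in any day row cannot exceed 50. The rate and interval use n, so they are correct; the N printed beside them is three times too large for the row.

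**Effect of the mixed unit in Freq.** Suppose 5 of 50 participants are positive on all three days. Counting occurrences over visits gives 15/150 = 10%. Counting distinct subjects over visits gives 5/150 = 3.3%. Counting by day gives 5/50 = 10%.

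**The case against.** The best reply is that the by-day reading was meant throughout.

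- The block in SAP 7.2.2 concerns an individual visit, in the singular.
- SAP 7.2.1 creates a Day 1 label, which only day rows need.
- In SAP 7.2.5.3, overall means the participant-level rate, not pooled visits.
- The Table 4.1 note is true of a table with three day rows, where a patient appears once per row and up to three times in the table.
- Explaining Freq. in subjects fits the same reading.
- Big N does not enter the rate or the interval, and may be no more than a dataset-level count.

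Most of this stands. The by-day reading is at least as well supported as the pooled one, and under it no rate or interval changes.

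What it does not remove is the wording. A big N in visits does not suit a day row, and it differs from the population N of SAP 7.2.5.3. The mock shell might settle the layout, but it is not in the documents and the SAP itself says of it: "Note: Shell does not contain all items to be displayed". The allowance in SAP 7.2.2 to describe modifications in the study report permits a later change; it does not define the row now.

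A reader might infer more: that the SAP orders a pooled row with an invalid interval, or that the incidence objective as a whole is undermined. The documents support neither. No section orders a row pooled over days, although none rules it out, and the whole-study rates are counted in participants.

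**Conclusion.** The point holds as an inconsistency to reconcile, and it is minor. The consequence depends on the reading:

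- By day: rates and intervals are valid, with coverage about 97% in the settings tried. Only big N is wrong, by a factor of up to about three.
- Pooled over days: the interval is too narrow if daily status is positively correlated. At 50 participants, 10% and ICC 0.3 to 0.7, coverage falls to between about 90% and 82%. At 25 participants and 10% the loss is small up to ICC 0.3 (94%).

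The coverage figures are conditional on the pooled reading, the assumed ICC, the assumed number of participants and three visits each. They are not a prediction for this study. The intervals are descriptive and no decision rule uses them. The whole-study participant-level rates are not affected by this issue; nothing else about them was tested here.

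**What to change.** In SAP 7.2.2, state that visit-level rates are shown as separate Day 1, Day 2 and Day 3 rows, with:

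- N and n counted in participants, n being those assessed for that item on that day;
- Freq. as the participants with a Yes on that day;
- the continuity-corrected Wilson interval as already planned.

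Give any count pooled over days without a confidence interval. Align SAP 7.2.1, SAP 7.2.5.3 and the Table 4.1 note with these definitions.

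The cost is a few words and a few lines of code. If the by-day layout was intended, only N and the labels change. If pooling was intended, the intervals widen by a factor of about 1.8 in the example (18.9 / 10.3), which is the precision that one day's participants can give.
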